Method: This is a randomized control pilot study to determine effectiveness of GMT plus Attention Training in 50 Veterans with mTBI. The research design is a parallel study with randomization to treatment or control with test administration at pre/post and six months following treatment. A multiple linear regression model will be used to determine if there is a significant association between treatment effect and comorbidities such as PTSD, depression, anxiety, pain, sleep, substance abuse, etc.

4. Background:

Problem. TBI can be the beginning of a disease process that produces change that continue years after injury resulting in debilitating chronic TBI symptomatology^{1,2}. Some studies find that up to 30% of people that have sustained mTBI have persistent symptoms³. Persistent symptoms following mTBI have been related to diffuse axonal injury⁴ or neuroinflammatory reactions⁵. Enduring cognitive deficits after mTBI present barriers to full functional recovery and re-entry into societal roles. Executive dysfunction, poor attention-concentration, and memory difficulties are the most persistent disabilities faced by mTBI survivors^{6,7}. An estimate 44% of Veterans with mTBI also have PTSD⁸ with overlapping symptoms. Attention problems are reported by 50% of combat Veterans⁹ which are requisite for other cognitive processes that are vital to everyday functioning such as memory, problem solving, language skills, and the cognitive control of behavior. Associated comorbidities also impair cognition making it difficult to diagnose and treat Veterans with mTBI. These comorbidities include pain¹⁰, substance abuse¹¹, anxiety¹², depression¹³, fatigue¹⁴ and sleep disturbances¹⁵ that also specifically impact attention. Cognitive deficits are the most debilitating following mild to severe TBI and can lead to long-term disability and immense economic burden¹⁶.

Gaps in Knowledge.

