Primary measure: Computerized Tower of London (cTOL) total time, time to first move and optimal moves). We have found significant improvement in cTOL following GMT in previous cohorts of Veterans with blast-related mTBI and anticipate improvement following a combined intervention.

Secondary measure: Attention Network Task (ANT) reaction time and errors for one or all dissociable components of three attentional systems (orienting, alerting, executive control) following intervention. There is little understanding of components of impaired attention and how it impacts executive function; therefore, there is limited guidance in shaping cognitive training. We will conduct an experimental task (attention network task) that disassociates three attentional components (alerting, orienting, and executive control). We will specifically target the orienting component of attention that is problematic for Veterans with mTBI and PTSD^{24, 26}. Attentional processes are vital to goal-directed behavior. There is great potential in the use of these measures to identify individual differences (type of attention deficit) that could moderate treatment-related improvement and inform targeted interventions.

Hypothesis 2: Treatment gains will translate to functional activities compared to controls.

Primary measure of functional performance: test of grocery shopping skills (TOGSS) total time and optimal strategy use. The TOGSS captures efficiency in completing a real-world task and aligns with the strategy skills learned in GMT.

Secondary measure of community participation, the Community Reintegration of Servicemembers (CRIS) extent of participation. The CRIS demonstrated significant GMT treatment effect compared to controls in Veterans with mTBI. The combined treatment of attention training using drill training and implementing strategies to improve attention in a functional setting through GMT will potentiate treatment effect to functional activities. Measuring functional improvement through performance-based measures and self-report of engagement in activities will demonstrate treatment translation.

Tertiary analysis will be conducted on moderator variables: PTSD symptoms, Pain, History of Substance Abuse, Depression, number of concussions and combat exposure.

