Randomization Procedure: 25 of the Veterans will be randomized to treatment while 25 will engage in BHW/movies as control participants. The Pocock-Simon covariate adaptive randomization procedure will be used so that, for each PTSD severity category, approximately 50% (25/25) of Veterans are assigned to treatment group; consequently, there will be approximately equal proportion of PTSD participants assigned to the treatment and control groups.

Each group of the 25 treatment and 25 control participants will also be randomized to training to complete the Test of Grocery Shopping skills in a virtual setting (V-Mart) during session 7 or 8.

Intervention

GMT: is a 10-session intervention to improve planning and problem solving. Interactive Power Point modules are administered by a cognitive therapist. Each session builds on the steps of a five-stage planning and problem-solving strategy. Veterans will be taught to generate and verbalize the following five-steps: "stop-what am I doing?", "define the goal", "list the steps", "learn the steps"; then, "check-am I doing what I planned?" The five-stage strategy is then incorporated into a variety of activities in the laboratory and in-home assignments. At each session, the participant discusses utilization of the strategies in daily life and reviews progress. The following steps are taught during simulated tasks: 1) Identify Main Goal; 2) Break down task into sub-goals and steps for each goal; 3) List supplies needed; 4) Recognize potential barriers to completing goal; 5) Determine strategy to accomplish task; 6) Prepare to begin task with "presence of mind" exercise; 7) State goal out loud; 8) Begin task and stop self frequently to state main goal out loud and check to be sure one is working toward the goal (on target).

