For both Hypothesis 1 and 2: A multiple linear regression model will be used to determine if there is a significant difference between the treatment and control groups in tests of cognition and function. Separate models will be fit for each outcome measure (cTOL, ANT, TOGSS, CRIS) the baseline measure and treatment group indicator will be used as covariates in the model. The Wald test will be used to determine if the coefficient for treatment group is significantly different from zero, indicating a significant treatment effect. Effect sizes for between-group differences will be estimated using the coefficient of the group indicator in the model.

Tertiary analysis: Other moderator variables (Table 2) will be examined to determine whether a linear relationship exists between changes in problem solving, attention or participation. These variables include PCL-5 total score and index scores (such as intrusions), BPI total score, AUDIT-C total score, BDI-II total score, number of concussions, STAXI-2, PSQI, MFIS and CES total score.

Sample Size: A sample size of 50 participants equally randomized into treatment or control groups will yield 80% power to detect an effect size of 0.81³⁹. In other words, if the true improvement in the treatment group is 0.81 standard deviations greater than the control group, then the pilot study has an 80% chance of detecting a significant difference. Based on our preliminary analysis of 14 GMT and 3 BHW controls, we estimate a large effect size of 1.76 (3.16, 0.37) for the cTOL time to first move, a moderate effect size of 0.827 (-0.46, 2.10) for cTOL optimal moves, and a moderate effect size of 0.67 (-0.60, 1.95) for cTOL time to completion⁴⁰.

7. Possible Discomforts and Risks:

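### PTSD severity category drives the allocation but is left out of the treatment-comparison models, which forgoes precision if PTSD predicts outcome beyond the baseline score

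*Combined protocol and SAP*

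**What the plan says.** Section 6, Randomization Procedure: "The Pocock-Simon covariate adaptive randomization procedure will be used so that, for each PTSD severity category", about half of the Veterans go to each arm, with the stated consequence that "there will be approximately equal proportion of PTSD participants assigned to the treatment and control groups". PTSD severity category is the only balancing factor named. The number of categories and their cut-points are not given.

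Statistical Analysis Plan, Hypotheses 1 and 2: separate linear regressions are fitted for cTOL, ANT, TOGSS and CRIS, and "the baseline measure and treatment group indicator will be used as covariates in the model". For inference, "The Wald test will be used to determine if the coefficient for treatment group is significantly different from zero". The reference distribution (normal or t) is not stated.

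PTSD appears elsewhere only as a comorbidity or moderator. The Abstract describes a regression to "determine if there is a significant association between treatment effect and comorbidities such as PTSD". Section 5 says "Tertiary analysis will be conducted on moderator variables: PTSD symptoms, Pain, History of Substance Abuse, Depression, number of concussions and combat exposure". The tertiary paragraph of the Statistical Analysis Plan lists PCL-5 scores among the moderators. No section adds PTSD category to the Hypothesis 1 and 2 models, and no re-randomisation test is planned.

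**The concern.** Balancing the arms on a prognostic factor removes most of that factor's contribution to the chance variation of the treatment difference. A model that omits the factor still counts its contribution in the residual variance. The reported standard error then exceeds the true sampling variability under this allocation, and the test rejects too rarely. The separate moderator regressions do not repair this, because they leave the standard error of the group coefficient in the main models unchanged.

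Precision is scarce at 25 per arm. The plan needs an effect of 0.81 SD for 80% power. Its preliminary estimates for two of the three cTOL measures are 0.827 and 0.67, both with intervals that include zero. Section 5 also gives a reason to think PTSD may matter, since it links PTSD to altered attention and treats attention as the gateway to executive function.

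**Working it through.** **1. The plan's own figure.** Inputs from the Sample Size paragraph: 25 per arm, effect 0.81 SD. Alpha is not stated; two-sided 5% is assumed.

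- Standard error of the difference in SD units: √(2/25) = 0.283.
- Normal approximation: 0.81/0.283 − 1.96 = 0.904, giving power 81.7%.
- Noncentral t with 48 df: 80.1%.

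The stated 80% is reproduced. One-sided 5% would give 88.1% and does not match.

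**2. Closed form under perfect balance.** Let R² be the share of outcome variance left after baseline that PTSD category explains. With residual SD 1 after baseline:

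- standard error reported without PTSD: √(2/25) = 0.283
- true standard error: √((1 − R²) × 2/25)
- ratio k = 1/√(1 − R²)
- size without PTSD: 2 × [1 − Φ(1.96k)]
- detectable effect with PTSD in the model: 0.81 × √(1 − R²)

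At R² = 0.20 the true standard error is 0.253 and k = 1.118. Size is 2 × [1 − Φ(2.191)] = 2.8%. Power without PTSD is Φ(0.81/0.253 − 2.191) = 84.4%; with PTSD it is Φ(0.81/0.253 − 1.96) = 89.3%. These are normal approximations and run slightly high.

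**3. Simulation of the allocation.** Assumptions not in the documents: three equally likely PTSD categories, probability 0.8 of assignment to the lagging arm, baseline coefficient 0.6, no dropout, and the R² values shown. The effect is 0.81 residual SDs after baseline, with a t reference. There were 30,000 runs per cell (Monte Carlo standard error about 0.13 points for size and 0.23 for power).

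| R² | Model SE / true SD, without PTSD | Size without PTSD | Power without | Power with | Detectable effect with |
|---|---|---|---|---|---|
| 0 | 1.00 | 5.1% | 79.1% | 79.0% | 0.81 |
| 2% | 1.02 | 4.9% | 79.7% | 80.1% | 0.80 |
| 5% | 1.03 | 4.5% | 79.7% | 81.1% | 0.79 |
| 10% | 1.05 | 4.1% | 80.2% | 83.1% | 0.77 |
| 20% | 1.10 | 3.1% | 81.2% | 87.0% | 0.72 |
| 30% | 1.17 | 2.2% | 82.5% | 91.1% | 0.68 |

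With PTSD in the model, size is 4.9 to 5.1% throughout. The mean estimate is 0.81 in every row, so there is no bias.

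**4. Sensitivity.** Two categories, or assignment probability 0.7 or 1.0, move size and the power gain by at most 0.3 point each. With 20% random dropout, the power change from adding PTSD at the six R² values is −0.6, −0.2, +1.0, +3.1, +7.5 and +11.6 points. A separate simulation with two or three categories and probability 0.8 or 1.0 gives, at R² = 20%, size 2.9 to 3.2% without PTSD and power rising from 81–83% to 87–88%.

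**5. Reference distribution.** A normal-reference Wald test at 47 df has size 5.6% when nothing is omitted. With that reference, simulated size without PTSD is 5.7, 5.4, 5.1, 4.6, 3.5 and 2.6% across the same R² values. Up to about R² = 5%, the slight liberality of the normal reference masks the conservatism.

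**The case against.** The strongest reply is that nothing the plan promises fails. The estimate is unbiased, false positives are not inflated by leaving PTSD out, and power as planned stays at about 79 to 83% across the assumed range. All of that stands; what is lost is attainable precision, in a pilot.

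Second, the documents give no R². A link between PTSD and attention level may be largely absorbed by the baseline score, and it bears more directly on ANT, a secondary measure, than on cTOL or TOGSS. Treating PTSD as a moderator of response also says nothing about its main effect. An R² of 20 to 30% is a partial correlation of about 0.45 to 0.55, which no section supports. This stands as a limit on the size: at R² of 10% or less the gain is at most about 3 points.

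Third, the gain depends on the reference distribution. Compare a normal-reference test of the plan's model with a t test that includes PTSD. The net power change is then about −1.6, −1.1, −0.2, +1.0 and +4.0 points at R² of 0, 2, 5, 10 and 20% (10,000 runs per cell, Monte Carlo standard error about 0.4 point). The figures are fair, but the loss at low R² comes from correcting a slightly liberal test, not from adding PTSD. On the same reference distribution, the covariate costs about 0.1 point when PTSD is not prognostic.

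Fourth, the covariate is not yet defined. That is true, and the allocation procedure itself needs the definition.

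**Conclusion.** The point holds in its conditional form. The models omit the one factor named for balancing, and no other planned analysis makes up for it. To the extent that PTSD category predicts an outcome beyond its baseline score, the t-based test is conservative and power is forgone: about 1 point at R² = 5%, 3 at 10%, 6 at 20% and 9 at 30%, and none at 0 to 2%. These sizes rest on assumed values for R², the categories and the assignment probability. The effect may be close to nil for some outcomes. This is an improvement the sponsor should make because it is almost free; it does not invalidate the planned analysis.

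**What to change.** Prespecify one model for every primary and secondary outcome: outcome = baseline value of that outcome + treatment group + PTSD severity category. Enter the category as a categorical covariate, exactly as used in the allocation. State in the Statistical Analysis Plan how the allocation defines the categories, and that the group coefficient is tested against the t distribution. Settle this before outcome data are examined, so that the covariate cannot be seen as chosen on results.

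The cost is a few sentences. The plan's model leaves 50 − 3 = 47 degrees of freedom; two or three categories use one or two of them. That alone moves noncentral-t power at 0.81 from 80.1% (47 df) to 80.0% (45 df). If PTSD is not prognostic, the simulated loss is 0.1 point, and at most 0.6 point in the sensitivity runs. No new data are needed.

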Control Group: Participants that are randomized to this group will provide a control for repeat testing and will provide similar characteristics with the treatment group, such as severity of PTSD. To equate for time and exposure to therapist, the participants will engage in a Brain Health Workshop (BHW) and watch geographic movies. BHW was developed specifically for consistency with GMT session length and contact with the facilitator⁴⁹. BHW is an education presentation on brain function and cognitive principles of learning with homework (readings assigned) and quizzes on information covered. To match time and contact of attention training, control participants will meet with the therapist for a separate two-hour session from BHW and watch geographic movies followed by a short quiz. This will equate the amount of time and contact experienced by the treatment group for both the GMT and attention training sessions.

Measurement: Veterans with mTBI will qualify for the study if they demonstrate a deficit in attention as measured by formal neuropsychological testing and pass effort testing. The following measures (Table 2) will be administered at week 1 (before intervention), week 11 (after intervention) and at week 36 (six months after intervention). The primary outcome measures for Aim 1, will be the computerized Tower of London (cTOL)³⁸ and the Test of Grocery Shopping Skills (TOGGS).

The following measures will be administered by an email link from the University of Florida REDCap application: Combat Exposure Scale, Neurobehavioral Symptom Inventory, Beck Depression Inventory, Alcoholic Use Disorders Identification Test, PTSD Checklist for DSM5, Brief Pain Inventory, Behavioral Rating Inventory of Executive Function for Adults, and State Trait Anger Expression Inventory.

Table 2. Study Measures			
Domain	Purpose	Administration session	Measure(s)/Minutes to Administer
Pre-Treatment Screening/Assessment			
Attention	Attention impairment	Weeks	RBANSAttention index
Effort	Determination of potential suboptimal effort	1	*TOMM/5
Word-reading	For group matching—estimation of pre-morbid cognitive ability	1	*NAART/10
Primary Outcome Measures			
Executive Function	Assesses problem-solving, planning and attention	1, 11, 36	cTOL/20
Functional	Assess performance of a complex task	1, 11, 36 7 or 8	ToGSS./30 V-Mart/20
Secondary Outcome Measures – Cognition			

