Attention	Behavioral performance associated with dissociable attention networks—alerting, orienting, executive control	1, 11, 36	ANT/ 20
Social Role Participation	Evaluate involvement and participation in life situations	1, 11, 36	CRIS/5
Tertiary Outcome Measures			
Moderating Variables	PTSD symptoms, pain, history of substance abuse, Depression, number of concussions, combat exposure, anxiety, fatigue, sleep.	1, 11, 36	*PCL-5/ 5, BPI/ 2, *AUDIT-C/2, *BDI-II/ 5, *OSU-TBI/5, *CES/ 5, *NSI/ 5, *STAXI-2/5, *MFIS/3, *PSQI/5
Cognition	Overall cognitive function	1, 11, 36	RBANS/20
Executive function	Secondary measure of executive function, attention and symptom reporting	1, 11, 36	EXAMINER/ 30, *BRIEF-A (self and informant report)/10
Functional Tasks	Attaining functional goals in attention and executive function	7 or 8	GAS/5, VTM-APP/task dependent
Usability	Evaluate user satisfaction of GMT, APT-III, Brain HQ and VTM-APP	11	TSQ/ 2
Usability	Patient logs sleep/wake times	1, 11, 36	CSL/2
Total Administration Time			Session 1: 179 minutes or 3 hours
Abbreviations: Attention Network Task (ANT); Alcohol Use Disorders Inventory (AUDIT-C); Beck's Depression Inventory (BDI-II); Brief Pain Inventory Short Form (BPI); Behavior Rating Inventory of Executive Function-Adult (BRIEF-A); Combat Exposure Scale (CES); Community Reintegration in Service members (CRIS); Consensus Sleep Log (CSL); computerized Tower of London (cTOL); Executive Abilities: Measures and Instrument for Neurobehavioral Evaluation and Research (EXAMINER; an NIH Toolbox measure); Goal Attainment Scale (GAS); Modified Fatigue Impact Scale (MFIS), Neurobehavioral Symptom Inventory (NSI); North American Adult Reading Test (NAART); Ohio State University-TBI identification Method (OSU-TBI); Pittsburgh Sleep Quality Index (PSQI); Post Traumatic Stress Disorder Checklist (PCL-5); Repeatable Battery for the Assessment of Neuropsychological Status (RBANS); State Trait Anger Inventory (STAXI); Test of Grocery Shopping Skills (ToGSS); Test of Memory Malingering (TOMM); Technology Satisfaction Questionnaire (TSQ); Virtual Reality Market (V-Mart); Veteran's Task Manager Smartphone Application (VTM-APP). *Common Data Element measures.			

Description of Measures

1. Screening Measures:

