National Adult Reading Test (NART) is an oral reading test consisting of 50 words (Nelson and Willison, 1991). The NART can be used to estimate premorbid intelligence and will be used as a screen. Similar to Levine et al. (2007), we will use the cut off score of > 90 as an inclusion criterion to ensure that frontal lobe impairment is not the result of low premorbid intelligence, and that the subject will be able to read the material during treatment.

Test of Memory Malingering (TOMM): is frequently used to detect poor effort on neuropsychological assessment and has been validated with TBI patients (Tombaugh, 1996; Slick et al., 2004; DeBoar, 2007). This test will be used to screen out patients scoring 45 or below on Trial 2 or the Retention Trial (Trial 1 scores will not be used) to provide a level of confidence to the results of outcome measures.

Repeatable Battery for the Assessment of Neuropsychological Status (RBANS): is a cognitive screening instrument The RBANS is composed of 12 subtests that yield 5 index scores and a total score. The subtests of List Learning and Story Memory comprise the Immediate Memory Index; Figure Copy and Line Orientation yield the Visuospatial/Constructional Index; Picture Naming and Semantic Fluency yield the Language Index; and Digit Span and Coding comprise the Attention Index. Four subtests make up the Delayed Memory Index, specifically, List Recall, List Recognition, Story Recall, and Figure Recall (Randolph, Tierney, Mohr, & Chase, 1998). Administration is approximately 20 minutes and has been used to assess cognition in mTBI (Cooper et al., 2010). An attention score of 1.5 SD below the mean will be used to include participants with an attention deficit. The index scores of the RBANS will also be used to characterize the patient's cognitive capacity and to determine whether aspects of cognitive ability impact response to treatment.

2. Primary Treatment Outcome Measures:

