EXAMINER: A battery of 10 executive function tasks have developed by a NINDS funded project to use in clinical research studies. The tasks take approximately 60 minutes to administer via a computer and result in 12 primary variables. Tasks include: Dot counting (count blue dots on a series of screens and recall the number of dots across screens), N-back (identify whether a series of locations match the location presented 1 or 2 before), Flanker (indicate the direction of an arrow that is flanked by arrows pointing in the opposite direction), Continuous Performance Test (respond to certain stimuli and withhold response to other stimuli on a computer screen), Anti-saccades (move eyes toward a stimulus and moves eyes away from a stimulus), Set-shifting (switch between a homogeneous matching task and a heterogeneous matching task), Phonemic Fluency (name as many words as possible with the same letter), Category Fluency (name as many items as possible in a category), Unstructured Task (complete puzzles within 6 minutes with the goal of earning as many points as possible), and the Social Norms Questionnaire (answer yes no questions about socially appropriate behaviors). Test re-test reliability is .94 and correlated with the FrsBe -0.57 in a multi-neurologic population.

Behavior Rating Inventory of Executive Functions–Adult (BRIEF-A) is a self and informant report questionnaire consisting of 75 statements about executive behaviors. There are three possible responses to items: often, sometimes, never. There are nine subscales: inhibit, self-monitor, plan/organize, shift initiation, task monitor, emotional control, working memory, and organization of materials. Normative self-report (n=1,050) reliability ranges from .73 to .90 for the scales and .93 to .96 for Index and Global Executive Composite scores. While the reliability in a mixed clinical sample (n=233) ranged from .80 to .94 for scales and .96 to .98 for Index and Global Executive Composite scores. Test-retest reliability over 4 weeks averaged .82 to .93 on the scales and .94 for Index and Global Executive Composite scores. The total BRIEF-A score correlates at .84 with the Dysexecutive Questionnaire (Roth, 2005). In a sample of patients diagnosed with TBI, the MI reported a cronbach alpha of 0.96 (Waid-Ebbs et al., 2012). The Metacognitive Index score of the BRIEF-A will be used to detect generalization of treatment effect and impact of specific executive function deficits on treatment gain.

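### The tertiary moderator analysis specifies no treatment-by-moderator term, so analyses that fit its wording could report prognosis as moderation

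*Combined protocol and SAP*

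**What the plan says.** The abstract (section 3, Method) plans a multiple linear regression to "determine if there is a significant association between treatment effect and comorbidities such as PTSD, depression, anxiety, pain, sleep, substance abuse". Other sections carry the same intent. Section 5 hopes that the type of attention deficit will moderate improvement under treatment. In the Description of Measures, the RBANS indices are to "determine whether aspects of cognitive ability impact response to treatment", the BRIEF-A is to show the "impact of specific executive function deficits on treatment gain", and the ANT, PCL-5, AUDIT-C and PSQI entries also speak of treatment effects or treatment response.

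The SAP's tertiary paragraph reads: "Other moderator variables (Table 2) will be examined to determine whether a linear relationship exists between changes in problem solving, attention or participation". It then lists nine variables: PCL-5, BPI, AUDIT-C, BDI-II, number of concussions, STAXI-2, PSQI, MFIS and CES. The only model with stated terms is the one for Hypotheses 1 and 2, where "the baseline measure and treatment group indicator will be used as covariates in the model".

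On timing, the Measurement section says that the Table 2 measures "will be administered at week 1 (before intervention), week 11 (after intervention) and at week 36 (six months after intervention". The moderator row of Table 2 shows the same three visits. No section says which visit supplies the moderator value.

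**The concern.** A factor can go with change in outcome for two reasons. It may predict change equally in both arms (prognosis), or it may alter how much treatment adds over control (moderation). Only a comparison of slopes between arms separates the two. The stated questions concern moderation, but the stated method is a linear relationship involving changes, with no second term and no product with treatment.

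An analyst could follow the sentence faithfully and still not address the abstract's question. A prognostic slope is a correct answer to a different question, and it misleads only if reported as moderation. That risk is real here because section 5 hopes to inform targeted interventions and section 8 offers treatment matched to particular components of attention.

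**Working it through.** **Text.** No section contains a product term, a comparison of slopes between arms or a subgroup contrast. The abstract's regression would allow an interaction but does not state one.

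**Design inputs (SAP, Sample Size).** 50 participants, 25 per arm, effect 0.81 SD, 80% power. Alpha is not stated; two-sided 0.05 is assumed. Normal approximation: Φ(0.81/√(2/25) − 1.96) = Φ(0.904) = 81.7%. The noncentral t gives 80.1%. The plan's figure reproduces; one-sided 0.05 would give 88.1%.

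**Further assumptions.** The documents give no moderator slopes. Take a standard normal moderator, within-arm SD of change 1 and treatment effect 0.81. Slopes then equal within-arm correlations.

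**No moderation, r = 0.3 in both arms.** Fisher-z approximations, with simulation (20,000 runs) in brackets:
- Pooled correlation. The arm difference adds 0.81²/4 = 0.164 to the variance of change, so r falls to 0.3/√1.164 = 0.278. Φ(atanh(0.278)·√47 − 1.96) = Φ(0.00) = 50% [50%].
- Treated arm only. Φ(atanh(0.3)·√22 − 1.96) = Φ(−0.51) = 31% [32%].
- Covariate with group, no product. Φ(atanh(0.3)·√46 − 1.96) = Φ(0.14) = 56% [56%].
- Interaction. No true difference in slopes, so 5% [5%].

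Simulated rates of significance over a range of correlations, no moderation:

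| Within-arm r | Pooled | Treated arm only | Covariate, no product | Interaction |
|---|---|---|---|---|
| 0.1 | 10% | 8% | 11% | 5% |
| 0.2 | 25% | 16% | 28% | 5% |
| 0.3 | 50% | 32% | 56% | 5% |
| 0.4 | 77% | 53% | 83% | 5% |
| 0.5 | 93% | 75% | 96% | 5% |

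**True moderation, slopes +0.4 (treated) and −0.4 (control).** The slopes cancel when pooled, and the simulated pooled test is significant in 7%. For the interaction, SE ≈ √(2 × (1 − 0.16)/22) = 0.276. The ratio is 0.8/0.276 = 2.90, and Φ(2.90 − 2.01) = 81% [81%; 80% with baseline adjustment, assumed coefficient 0.5].

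**What an interaction test can do at this size.** For a slope difference of 0.5, power is 39% to 42%, depending on how the slopes split between arms. With an assumed 40 completers it is about 34%. Power reaches 80% only at a difference of about 0.8. Median 95% CI half-widths are 0.52 to 0.60 SD of outcome per SD of moderator. Fixing the residual SD at 1, rather than the total within-arm SD, changes little: 80% power by formula needs 0.81, and simulated power at 0.8 is 74%.

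**Multiplicity.** Nine moderators × three outcomes at one score each = 27 models per visit, and 27 × 0.05 = 1.35 intervals excluding zero by chance. Section 5 names three cTOL variables, ANT reaction time and errors for three networks (6), and CRIS extent (1), which is 10 scores. Then 9 × 10 = 90 models, and 90 × 0.05 = 4.5.

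**The case against.** The strongest reply is that calling these variables moderators already implies an interaction, and that the abstract names regression on the treatment effect. The word does show intent, but it fixes no model, and three analyses that do not test moderation satisfy the SAP sentence. What stands is that the sentence is incomplete. A reader might infer that the plan has committed itself to a prognostic analysis. It has not, because the second term is missing and an interaction model remains compatible with the abstract.

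Two further readings are tempting and should not be made:
- **Visit.** A reader might infer that leaving the visit open inflates false positives. If treatment shifts a week-11 scale by an assumed 0.2, 0.5 or 0.8 SD and the scale is unrelated to change within arms, a pooled test is significant in 6%, 10% and 16%. With group in the model, as in the SAP's main models, the moderator test gives 5.1%, 5.0% and 4.7%, and the interaction test 5.2%, 5.3% and 4.9%. No inflation remains. The surviving point is about interpretation: a value that treatment may have changed is hard to read as a moderator. This hardly touches concussion count and combat exposure, which are largely historical.
- **Lists.** A reader might infer that the moderator lists conflict. The SAP sentence refers to Table 2 and its list is open-ended, so the NSI, in the Table 2 run "CES/ 5, *NSI/ 5, *STAXI-2/5, *MFIS/3, *PSQI/5", is already covered. The heading over these measures also allows some to serve only to characterise participants.

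It is also fair that this is a tertiary analysis in a pilot and that a correct interaction test will be imprecise. That argues for exploratory reporting with intervals, not for an analysis that answers another question.

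**Conclusion.** The concern holds as a minor correction. The documents ask about moderation, the SAP describes an unfinished linear relationship with change, and no treatment-by-moderator term appears anywhere. Analyses that fit the wording would flag a purely prognostic factor in about 32% to 56% of trials at a within-arm correlation of 0.3. The range is 8% to 11% at 0.1 and 75% to 96% at 0.5, against 5% for the interaction test throughout. A pooled analysis could also miss real moderation (7% against 81% at slopes +0.4 and −0.4). All slopes are assumptions, as are two-sided 0.05 and unit within-arm SD.

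A reader might infer that this weakens the trial's treatment comparisons. It does not: the primary and secondary models contain baseline and group and do not depend on the tertiary analysis.

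**What to change.** Replace the tertiary sentence with text such as:

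> For each moderator we will fit outcome = baseline outcome + group + week-1 moderator + group × week-1 moderator, using one pre-named score each for problem solving (cTOL), attention (ANT) and participation (CRIS). Where the moderator is itself the baseline outcome, it is entered once, plus its product with group. Interaction estimates with 95% CIs are exploratory, and the number of models fitted will be reported.

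Use the same outcome visit or visits as the main models.

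**Cost.** SAP wording and two extra terms per model. Week-1 values of the nine listed variables are already scheduled, so no instrument or visit is added for them. The downsides are the low precision and the chance findings shown in the working. The one-score limit must be in the text, because without it the count rises from 27 models towards 90 per visit, and more if PCL-5 index scores are used.

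**Optional housekeeping.** Settle whether the ANT networks, RBANS indices and BRIEF-A Metacognitive Index belong in the list. Table 2 names anxiety among its constructs ("number of concussions, combat exposure, anxiety, fatigue, sleep"), but no instrument in that row is described as measuring it, so it should not be treated as already collected.
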